## Part 2 - Survey recruitment

Both healthcare providers and patients will be invited to take part in the Discrete Choice Experiment, sample size is 200 with a minimum of 50 responses being by health care professionals. We will invite up to 150 patients who attend the Manchester University NHS Foundation Trust Breast Service to participate in the study. These will be patients who have undergone breast cancer surgery and so have some insight into the treatment pathway. The patients will be invited either before or after their clinic appointment to complete the survey. Participants will be recruited by research staff while present for a clinical appointment in the Nightingale centre. Upon consenting to hear about the study, patients and healthcare providers will be given a short synopsis of the study detailing the aims and providing a brief example of the survey questions, in the form of a patient information leaflet (paper or electronic). Following consent (either by paper forms or using a Tablet-PC), respondents will be asked to spend 10-15 minutes completing the survey. Informed consent will be implied via completion of the survey both online and paper. No patient identifiable information will be collected for the survey, only very basic baseline demographics including age (patients), role (in the case of healthcare providers) and how far they have travelled to the department that day (patients).

A minimum of 50 Healthcare providers will be invited to complete the survey electronically, this will be a mixture of breast surgeons, breast care nurses and breast radiologists. They will be invited via email, directly from the study team. This is a survey to establish their preferences towards the healthcare scenarios provided to them, as such their answers will be critical to understanding the perceived added value of Magtrace. These individuals will be given written information about the study as with the patients, in the form of a participant information sheet, and asked to complete a consent form to take part in the study (either by paper forms or using a Tablet-PC). Informed consent will be implied via completion of the survey both online and paper. No identifiable information will be collected about the respondent with the exception of some simple descriptors and demographics. A full step by step guide to this process is provided in Figure 4

[figure not shown]

Figure 4: Study flow for DCE

#### 4.3 Gantt Chart

Discrete Choice Experiment

## 5. Selection and Withdrawal of Subjects

#### 5.1 Informed Consent

Consent for Part 1 of the study will be taken by a Consultant Breast Surgeon or Research Nurse. This consultant or research nurse will be authorised to take consent by the Chief Investigator of the study and will have received training about the study and written information about the study. This consent process will take place at Study Visit 1, for Part 1 patients, more than 24 hours after initial invitation to take part in the study. Consent for Part 2 (Focus Group & Survey) will be undertaken by the same staff members but will be taken at the time of introduction of the study to the patient or healthcare professional.

## 5.2 Inclusion Criteria - Part 1

- Participant is willing and able to give informed consent for participation in the study;
- Female, aged 18 years or above;
- Diagnosed with invasive breast cancer
- Willing to allow his or her General Practitioner and consultant, if appropriate, to be notified of participation in the study;

- Undergoing breast conservation surgery requiring Magseed® localisation and sentinel node biopsy
- All MRIs must be completed prior to Magseed® insertion

#### 5.3 Exclusion Criteria – Part 1

- Patients with a Pacemaker or implanted device in the chest wall;
- Patients who are pregnant or lactating;
- Patients who have received Magtrace® (iron oxide) injection in the previous six months;
- Patients with previous ipsilateral axillary surgery
- Patients whose breast and axillary surgery are not due to be performed synchronously.
- Patients following neoadjuvant chemotherapy
- Patients requiring an interpreter
- Patients involved in current research or have recently been involved in any research prior to recruitment

Patients who require MRI follow-up of the ipsilateral breast in the year following surgery (as Magtrace® may interfere with MRI)

All individuals will be considered for inclusion in this study regardless of age, disability, gender reassignment, marriage and civil partnership, pregnancy and maternity, race, religion and belief, sex, and sexual orientation except where the study inclusion and exclusion criteria EXPLICITLY state otherwise

# 5.4 Screening and Eligibility Assessment

Potential participants for Part I will be identified at the Breast Multidisciplinary Meeting which occurs every morning in the Nightingale Breast Unit, MFT. Potential study participants will be patients who are newly diagnosed with breast cancer and screening will occur in this pre-clinic MDT meeting to see if they meet the eligibility criteria for the study. These patients will have a clinical consultation with a Breast Care Nurse and Breast Surgeon later the same day and their cancer diagnosis and care will be discussed. At the end of this discussion they will be offered further discussion about this study which they could be eligible for. The study will be briefly introduced by the clinician and then if the patient is potentially interested, they will be given a Patient Information Leaflet about the study and made aware that the study is completely

Title: Costs and benefits of Magtrace® in breast surgery Protocol V1 Date 03/08/2022

IRAS 293053 Page 31 of 45

optional and in the next few days the Research Nurse will contact them to ask if they are potentially interested in taking part.

Patients interested in taking part in the study will return for a further follow-up visit to discuss the study further and to confirm eligibility and to consent to the study at this point.

The screening process will include collection of the following data;

- Demographics age, sex, BMI;
- Current medications including anticoagulant medication;
- Pre-operative histology of the breast cancer;
- Oncological information size and location of lesion on imaging, clinical findings, radiological score;
- Medical history including implantable devices such as pacemakers or defibrillators:

#### Part 2 - Focus Groups

Potential participants will be identified by the Research nurses and surgical team at the Breast Multidisciplinary Meeting which occurs every morning in the Nightingale Breast Unit, Manchester University NHS Foundation Trust. Patients will be approached during their appointment at Manchester University NHS Foundation Trust for the study design part of the discrete choice experiment. Healthcare professionals will be approached via either direct contact with the research team or by electronic invitation from the Chief Investigator. Informed consent will be taken on paper at time of introduction to the study.

#### Part 2 - Survey

Patient participants will be recruited by research staff while in waiting room of the Nightingale centre. Upon consenting to hear about the study, patients and healthcare providers will be given a short synopsis of the study detailing the aims and providing a brief example of the survey questions. Following verbal consent to complete the survey, respondents will be asked to spend 10-15 minutes completing the survey. Informed consent will be implied via completion of the survey both online and paper. No patient identifiable information will be collected for the survey, only very basic baseline demographics including age (patients), role (in the case of healthcare

providers) and how far they have travelled to the department that day (patients). Healthcare providers will be recruited by direct and email approach from the research team and by electronic invitation to complete the study online.

Please note the survey will be designed as part of the Focus Group meetings, the REC and HRA will be notified when the survey has been created via non-substantial amendment and a copy of the survey before being given to any participant for completion. The survey will not collect any personal information.

# 5.5 Selection of Participants

Case control study of 40-50 patients in the time in motion study and 200 (150 patients, 50 healthcare providers) in the Discrete-Choice Experiment (DCE). 5-10 patients will be invited to participant in the study design part of the discrete choice experiment.

## 5.6 Withdrawal of Subjects

Safety of the study participants will be monitored by the Chief Investigator. It is unlikely there will be Serious Adverse Events directly related to the study as all of the interventions are now established in large studies with good safety profiles. Magtrace® has a risk of causing staining to the skin of the breast in the months following injection and that it appears as a brown stain that fades over time. This is similar to the blue dye that is often used in conjunction with Technetium to help identify the sentinel nodes in existing practice. The blue dye stains the skin Blue/grey compared to the brown of Magtrace®. The blue dye has a 1 in 10,000 risk of anaphylaxis, a risk not seen in Magtrace® injection.

Each participant has the right to withdraw study at any time. In addition, the investigator may discontinue a participant from the study at any time if the investigator considers it necessary for any reason including:

- Ineligibility (either arising during the study or retrospective having been overlooked at screening);
- Significant protocol deviation;
- Significant non-compliance with treatment regimen or study requirements;
- An adverse event which requires discontinuation of the study medication or results in inability to continue to comply with study procedures;
- Disease progression which requires discontinuation of the study medication or

results in inability to continue to comply with study procedures;

- Consent withdrawn;
- Lost to follow up.

It is understood by all concerned that an excessive rate of withdrawals can render the study un-interpretable; therefore, unnecessary withdrawal of patients should be avoided. Should a patient decide to withdraw from the study, patients will asked for a reason for withdrawal if they wish to offer one.

Withdrawal from the study will result in exclusion of the data for that participant from analysis.

The reason for withdrawal will be recorded in the CRF.

If the participant is withdrawn due to an adverse event, the investigator will arrange for follow-up visits or telephone calls until the adverse event has resolved or stabilised.

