#### 3.2 Potential Risks to Patients

- All processes and technologies have previously been proven to be efficacious and effective.
- Technetium sentinel node injection is often combined with a blue dye to
  increase nodal yield. The blue dye has a small risk of anaphylaxis of
  approximately 1 in 10,000 and can stain the skin of the breast blue for several
  months. Magtrace® does not have a risk of anaphylaxis but can stain the skin
  of the breast brown for several months post-operatively.

Title: Costs and benefits of Magtrace® in breast surgery Protocol V1 Date 03/08/2022

Magtrace® is used as a single tracer whereas Technetium is either used as a single tracer or as a dual tracer with blue dye. Both methods are standard of care and their utility is dependent on the availability of one of the two dyes.
 I.e. if technetium not available Magtrace is used and vice versa. The number of nodes removed during Magtrace® localisation is slightly lower than that with Technetium, as proven on Meta-analysis (on average 1.9 nodes removed vs 2 with Technetium). This difference in tracer performance has not been shown to be clinically relevant or to increase the risk of lymphoedema in patients' index arm's as a result of removing slightly more lymph nodes in the case of Technetium.

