It will be the responsibility of the research assistants to provide a 'learned' assessment, of what they believe represents a 'typical' pathway at the Nightingale centre. A multidisciplinary team will then assess the validity of this pathway and voice any concerns/objections/potential additions. Once an accurate representation of the existing care pathway has been generated (as agreed by research staff and clinical leads), this will be pilot tested among a group of 10 patients (5 current SOC and 5 Magtrace), in order to ensure that all relevant points of interaction with healthcare staff, and utilisation of health services, are captured, the pathway will be amended as necessary. Using a stopwatch, research staff would have the ability to consent and then actively monitor (shadow around the hospital) a group of ~20 patients in each treatment group (Magtrace® vs. routine care using Technetium nuclear medicine). It is critical prior to recruitment that key covariates and factors likely to influence not only outcomes, but also health economic factors of care are identified. These factors will require consideration before randomisation to Magtrace or routine care, with randomisation recommended to take place using sealed envelopes in blocks of ten. If imbalances in key covariates occur following randomisation, adjustment of health economic outcomes will be performed to mitigate these imbalances using gold-standard two-stage bootstrapping for costeffectiveness analyses.

[figure not shown]
Once data is collected for 20 patients undergoing Magtrace, and 20 patients undergoing routine care, it will be possible to multiply NHS resource utilisation by representative NHS unit costs (staff salaries per minute, radiography, inpatient, nuclear medicine) and determine the array of health economic outcomes listed above. The result will be a health-economic comparison of Magtrace® over Technetium nuclear medicine (Figure 1). Sensitivity analyses will be performed on this dataset to measure the robustness of the findings to changes in the values of the parameters measured during the TDABC stopwatch exercise. Rather than relying on point-estimates, this will enable the derivation of credible intervals, and determine

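### Section 5.6 excludes every withdrawn participant from analysis, including those the investigator discontinues after randomisation, which can bias the cost comparison and the analysed tracer endpoints

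*Protocol*

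**What the plan says.** The exclusion rule stands in Section 5.6 of the protocol: "Withdrawal from the study will result in exclusion of the data for that participant from analysis". No reason for withdrawal, endpoint or type of data is exempted.

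The same section lets the participant leave at any time and adds that "the investigator may discontinue a participant from the study at any time if the investigator considers it necessary for any reason including" a list of reasons. Three of them matter here:

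- an adverse event, worded as "An adverse event which requires discontinuation of the study medication or results in inability to continue to comply with study procedures";
- a departure from the planned procedures, where it amounts to a "Significant protocol deviation";
- marked failure by the participant to comply with the treatment or with what the study asks.

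Part 1 is randomised: under Study design (Part 1) the text has "randomisation recommended to take place using sealed envelopes in blocks of ten". The visit list in Section 4.2 and the schedule in Section 6 place randomisation at Visit 1. Technetium follows at Visit 2a or 2, and Magtrace and surgery at Visit 2.

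Section 4.1 makes cost effectiveness the primary endpoint. Its secondary endpoints include tracer-related adverse events, detection of tracer in the nodes, and delays in getting patients to theatre.

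**The concern.** Randomisation protects the comparison only if patients stay in it for reasons unrelated to what happened after allocation. Deviations, non-compliance and adverse events all arise after Visit 1 and can differ between two tracers with different logistics and side effects. No blinding is described: the surgeon injects Magtrace, and research staff follow patients with a stopwatch. The decision to discontinue, and hence to exclude, lies with staff who can know the arm.

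The patients at risk of exclusion may also be the most informative about cost. Section 3 describes Technetium as scarce and hard to schedule, and Section 3.2 says of usual practice that "if technetium not available Magtrace is used and vice versa". If a supply-driven switch were judged a significant deviation, that patient's pathway could be excluded from the comparison meant to cost it. Study design (Part 1) then bootstraps from the 40 observed patients to a year's caseload and a Trust-level return on investment, so any selection would carry through to that result.

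**Working it through.** **1. Does the rule reach investigator discontinuations?** Yes. Section 5.6 describes a participant discontinued for an adverse event as withdrawn: "If the participant is withdrawn due to an adverse event, the investigator will arrange for follow-up visits or telephone calls". The exclusion sentence is framed on withdrawal without qualification.

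**2. Are these events after randomisation?** Yes, from the visit order in Sections 4.2 and 6.

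**3. Does another section override the rule?** I found no as-randomised analysis set, no safety set and no provision for data collected before withdrawal. Sections 10.1 and 10.3 only refer back to earlier text. The statistical analysis plan is not at hand, but one that kept these patients would contradict the protocol.

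**4. Size of the effect on the cost comparison.** The planned 20 per arm comes without SD, target difference, alpha, power or dropout rate, so it cannot be reproduced. The scale below is in SD units and assumes normal costs.

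- Standard error of the difference: √(2/20) = 0.316 SD.
- Excluding k of 20 patients in one arm, whose average lies D SD above the full-arm mean, lowers that arm's mean by kD/(20 − k).
- In the worst case the k costliest are removed. The expected top three order statistics of 20 standard normal values are 1.867, 1.408 and 1.131, with cumulative sums 1.867, 3.275 and 4.406.

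| k excluded, one arm | Shift in that arm's mean (SD) | Shift ÷ 0.316 |
|---|---|---|
| 1 | 1.867/19 = 0.098 | 0.31 |
| 2 | 3.275/18 = 0.182 | 0.58 |
| 3 | 4.406/17 = 0.259 | 0.82 |

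In a milder case with D = 1, the shifts are 1/19 = 0.053, 2/18 = 0.111 and 3/17 = 0.176 SD.

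**5. Effect on the error rate.** For each setting, 10,000 trials with no true difference were simulated (t-test, two-sided 5%). The k patients excluded from one arm ranked highest on a score with correlation ρ to cost.

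| k | Type I error, ρ = 0.5 | Type I error, ρ = 1 |
|---|---|---|
| 1 | 0.053 | 0.068 |
| 2 | 0.060 | 0.101 |
| 3 | 0.071 | 0.142 |
| 4 | 0.080 | 0.194 |

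With everyone analysed as allocated, the error rate was 0.047 to 0.054.

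**6. Effect on the binary endpoints (exact 95% limits).**

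- One patient withdrawn for a tracer-related event: 1/20 = 5% (0.1% to 24.9%) becomes 0/19 = 0% (upper limit 17.6%).
- Two such patients: 2/20 = 10% (1.2% to 31.7%) becomes 0/18 = 0% (upper limit 18.5%).
- One detection failure withdrawn as a deviation: 19/20 = 95% becomes 19/19 = 100%.

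**The case against.** The opposing case is strongest on four points.

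- **Deletion.** A reader might infer that data are destroyed. The text speaks only of exclusion from analysis. The reason for withdrawal goes into the CRF, and Section 15 provides for archiving of trial data. This objection stands.
- **Safety.** A reader might infer that the rule hides adverse events. It does not do so for reporting or oversight. Section 5.6 follows an event that led to withdrawal until it resolves or stabilises. Section 9 sends serious events immediately to the sponsor, names Magtrace allergy as reportable, and has the steering committee consider all serious and other adverse events. Only the analysed safety endpoint can lose the patient.
- **Tracer switches.** A reader might infer that a control patient whose Technetium did not arrive would be excluded. No section calls a switch a significant deviation. The sentence in Section 3.2 describes general practice, discontinuation is discretionary, and Section 5.6 asks that unnecessary withdrawals be avoided. The documents support only that such a patient could be excluded.
- **Size.** No withdrawal rate is given, and nothing shows that withdrawn patients would be the costliest or would all come from one arm. With moderate correlation and one or two exclusions, the error rate stays close to 5%. Tracers are given on or just before the day of surgery and the last visit is remote, so there is little treatment left to stop. This limits how often the rule would apply, but not what it does when it applies.

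None of these points removes the unconditional sentence or supplies an analysis set that contradicts it.

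**Conclusion.** The concern holds in this form: the protocol fixes an exclusion rule that depends on events after randomisation and partly on unblinded discretion. The rule can bias the primary cost comparison and the analysed tracer-safety and detection endpoints. This is a stated rule that is wrong as written, not detail left to an analysis plan.

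The shifts of 0.10 to 0.26 SD are an illustration. They assume normal costs, one to three exclusions, all in one arm, and always the costliest patients. Each is below one standard error of the difference, so they show that a few exclusions could matter in a trial of this size, not that bias of that size should be expected. The change from 1/20 to 0/19 needs only one excluded patient who had the event.

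**What to change.** Replace the exclusion sentence in Section 5.6 with:

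> All randomised participants are analysed in the arm to which they were randomised, using all data collected up to withdrawal, unless the participant asks for their data to be removed. Tracer switches and protocol deviations stay in the allocated arm with the costs actually incurred. Everyone who received a tracer is included in the safety summaries.

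Also:

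- report withdrawals and their reasons by arm;
- treat unobserved episode costs, such as those of a patient withdrawn before surgery, as missing data, with a sensitivity analysis;
- keep any per-protocol analysis as a sensitivity analysis only.

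The cost is about one paragraph of protocol text, plus a check that the participant information agrees with it. No extra patients and no change to care are needed.

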## 5.7 Expected Duration of Trial

Expected duration of patient participation in Part 1 – Four to eight weeks. This will equate to a 1-4 week period between invitation to join study and Study visit 3 when post-surgery histology is discussed. Study visit 1 will occur a minimum of 1 day prior to surgery. Surgery will not be delayed beyond 31 days from decision to treat the cancer. There will be a 2-3 week period between surgery and the final follow-up Study visit 3, the end of the study will be confirmed as when post-operative histology has been recorded and any plans for re-excision surgery are known.

Expected duration of participation in Part 2 Focus Group – 60 minutes.

Expected duration of participation in Part 2 Survey - 15-20 minutes.

#### 6 Trial Procedures – Part I

Assessments	Visit 2a	

	Baselin e Visit 1	Technetiu m (two day protocol only)	Surgery Visit 2	Post surgery Visit 3
		3,		
Informed consent and randomisation	Х			
Medical history	Х			
Magseed® insertion	Х			
CRFompletion including data transfer and query resolution	Х	Х	Х	Х
Concomitant medication check	Х			Х
Review/reporting of patient AEs/SAEs			Χ	Х
Anaesthetic assessment	Х			
Localise lesion with Magseed® during surgery			Х	
Perform sentinel node biopsy			Χ	
Data collection in theatre			Х	
Technetium injection		Х	X (one day protocol)	
Magtrace® injection			Х	

[figure not shown]

